6.5 Secondary Endpoint Analysis

The secondary endpoint of the study is the proportion of Subjects with an IGA success, defined as achieving a rating of ‘completely cleared’ (0) or ‘partially cleared’ (1) in IGA of AK status at Week 8. This analyses of IGA will be conducted using the FAS dataset.

6.6 Additional Analysis

6.6.1 *Treatment Satisfaction Analyses*

Subject’s satisfaction with tirbanibulin treatment at Weeks 8 and 24 measured using TSQM-9 will be analyzed for relevant groups of Subjects, using descriptive statistics (ie, mean, SD, median, minimum and maximum), for each of the three TSQM subscales, using FAS. Site Investigator’s satisfaction with tirbanibulin treatment at Weeks 8 and 24 measured using ad hoc questions that are similar to TSQM-9 will be analyzed for relevant groups of Subjects, similar to TSQM-9 employing descriptive statistics, using the FAS dataset.

Subject and Site Investigator’s satisfaction with the ability of AK treatment to ‘improve how skin looks’ and ‘improve skin texture’ will be respectively analyzed descriptively using data from Weeks 8 and 24, for relevant groups of Subjects, and frequency of responses will be assessed. Proportion of respondents who indicated ‘moderately satisfied or very satisfied’ on the response scales will be reported for these respective questions, using the FAS dataset.

Among Subjects who have experienced other topical treatments before start of tirbanibulin at baseline, Subject and Site Investigator’s rating of their ‘overall satisfaction’ with tirbainbulin treatment at Week 8 and Week 24, in comparison to previous topical treatments to treat Subject’s AK will be respectively analyzed descriptively using data from Weeks 8 and 24, and frequency of responses will be tallied for all Subjects. Proportion of respondents who indicated ‘somewhat better or much better’ on the response scale will be reported, using FAS. Similar analysis of ‘overall satisfaction’ with tirbanibulin in comparison to most recent topical treatment reported by

Subjects and Site Investigators will be performed for the subgroup of Subjects who are re-treated with another topical treatment (other than tirbanibulin) between Week-8 and Week-24, and descriptive results reported using FAS, along with the proportion of respondents who indicated ‘somewhat better or much better’ on the response scales.

6.6.2 Cosmetic Appearance of Skin

Subject and Site Investigator’s rating of overall appearance of the skin in the AK treated area at Weeks 8 and 24 will be respectively analyzed descriptively, and frequency of responses will be tallied for all Subjects. Proportion of respondents who indicated ‘somewhat improved or much improved’ on the response scale will be reported, using the FAS dataset.

6.6.3 Photodamage Severity Analyses

The proportion of Subjects with a severity of score of 0 (absent) and proportion of subjects with a severity score of 0 (absent) or 1 (mild) in clinician assessment of AK-related photodamage at baseline, and at Weeks 8 and 24 will be assessed respectively. CFB in photodamage severity score at Weeks 8 and 24 will be explored and reported using descriptive statistics. This analysis will be conducted using the FAS dataset.

6.6.4 Future Treatment Preference

Subject and Site Investigator’s statements (at Week 8 and 24) of their likelihood to consider tirbanibulin to retreat AK in the future will be respectively analyzed descriptively, and frequency of responses will be tallied for all Subjects. Proportion of respondents who indicated ‘somewhat likely or very likely’ on the response scale will be reported, using the FAS dataset.

6.6.5 Other Outcome Measures

Among Subjects who have experienced other topical treatments before start of tirbanibulin at baseline, the following outcome measures will be analyzed descriptively, and frequency of responses tallied for all Subjects:

- Subject and Site Investigator’s rating (at Week 8 and 24, for relevant groups of Subjects) of ‘convenience/ease of use’ associated with tirbanibulin treatment, in comparison to previous (or most recent) topical treatment(s) to treat their AK; proportion of respondents

who indicated ‘somewhat better or much better’ on the response scale will be reported using the FAS dataset.

- Subject and Site Investigator’s rating (at Week 8 and 24, for relevant groups of Subjects) of ‘duration of skin reactions’ associated with tirbanibulin treatment, in comparison to previous (or most recent) topical treatment(s) to treat their AK; proportion of respondents who indicated ‘somewhat shorter or much shorter’ on the response scale will be reported using the FAS dataset.
- Subject and Site Investigator’s rating (at Weeks 8 and 24, for relevant groups of Subjects) of ‘severity of skin reactions’ associated with tirbanibulin treatment, in comparison to previous (or most recent) topical treatment(s) to treat their AK; proportion of respondents who indicated ‘somewhat better or much better’ on the response scale will be reported using the FAS dataset.
- Subject and Site Investigator’s rating of how tirbanibulin (at Weeks 8 and 24, for relevant groups of Subjects) treatment impacted their daily activities due to skin reactions, in comparison to previous (or most recent) topical treatment(s) to treat their AK; proportion of respondents who indicated ‘somewhat better or much better’ on the response scale will be reported using the FAS dataset.

6.6.6 *Unscheduled Patient Encounters*

Number of unscheduled clinician encounters (via in-person clinic visits, telehealth visits and phone calls) that AK patient had in the past 8 weeks will be analyzed at Week 8 using descriptive statistics (i.e., mean, SD, median, minimum and maximum) and reported.

6.6.7 *Treatment Adherence*

Treatment adherence will be assessed (at Week 8) as the number of missed single-dose applications within the expected 5-day application period/regimen divided by five, the expected number of single-dose applications of tirbanibulin during the study observation period within first 8 weeks. Treatment adherence will be calculated for each subject, using the FAS dataset. Summaries will be presented using descriptive statistics for the Safety population.

Percentage Adherence = [1 - [# of missed single-dose applications out of 5] / 5]*100

6.6.8 Prior and Concomitant Medications

Medication usage is coded using the latest (2022) WHO Drug Dictionary. Medications are presented by WHO Drug Anatomical/Therapeutic/Chemical (ATC) category and WHO Drug preferred name. Summaries are presented for prior (prior to the first dose of study treatment, gathered as aggregate indicators as well as at individual item level) medication use and concomitant (after first dose of study treatment had been given, gathered at individual item level) medication use. Medications with an end date occurring before the first study treatment (tirbanibulin) date in the treatment period are identified as prior medications. Medications with a start date occurring on or after the first study treatment (tirbanibulin) date in the treatment period or medications with a start date prior to the first (tirbanibulin) dose that were ongoing or with end dates that were on or after 8 weeks post index date are identified as concomitant medications.

Concomitant AK and non-AK medications are captured at Baseline and at Week-8 to characterize the use of concomitant medications among the study cohort. Additional information is captured at Week-24 if the patient was re-treated with tirbanibulin, another topical treatment for AK, or a non-topical treatment for AK between the week-8 and week-24 timepoints.

All summaries present the number (%) of subjects for each medication. The denominators for calculating the percentages are based on the number of subjects in the FAS population.

6.6.9 Safety Assessments

The safety data will be analyzed descriptively using Safety Population dataset (if it is different from FAS), to report the frequency of occurrences of AEs, SAEs, ADRs, and LSRs. These will be reported at individual item level as well in aggregate at relevant category level for Week 8

post-index date. The number of patients discontinuing treatment within the 8-week post-index date because of AEs, ADRs and for any other reasons will be reported, as documented in patient medical charts.

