2 INTRODUCTION: BACKGROUND INFORMATION AND SCIENTIFIC RATIONALE

2.1 Background Information

Actinic Keratosis (AK) a common skin condition in which excessive and prolonged exposure to ultraviolet radiation. AK typically affects around 58 million people in the US and is more common in older adults, males, and those who are fair skinned. (Kempers et al, 2020). AK manifests as scaly, red lesions on face, trunk, scalp, and other sun exposed extremities; it could lead to epidermal lesions and eventually progress to squamous cell carcinomas (SCC) if left untreated (Khanna et al., 2017), with up to 65% of SCC arising from pre-existing AKs (Marks et al, 1988; Criscione et al, 2009). The rationale behind treating every AK lesion is based on the difficulty in predicting which single AK lesion will progress to SCC (Werner et al, 2015; Drake et al, 1995). The goal of treatment is to eliminate AK lesions, thereby minimizing their risk of progression to invasive SCC and reducing the associated morbidity and mortality, while obtaining the best cosmetic outcomes. While the clinical trials have compared the treatment outcomes of different therapies (Zane et al, 2016), patient reported outcomes (PROs), including patient preferences and what patients value the most for the AK treatment could improve total patient management in AK (Esmann et al, 2015, Siegel et al, 2017, Kopasker et al., 2019).

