5.3 Treatment Effectiveness Assessments

The effectiveness of tirbanibulin treatment will be assessed from the perspective of Site Investigators as well as the Subjects. It is expected that the Site Investigator assessments will be conducted via in-person visits/encounters at baseline, Week 8 and Week 24, and when in-person assessments are not feasible (owing to COVID-related travel restrictions), the assessments

maybe done via virtual/remote visits. The same evaluator at study site shall perform all evaluations for a subject during the study, as feasible.

5.3.1 *Investigator Global Assessment (IGA):*

Site Investigators to assess the status of subject's AK in the treated area on the face or scalp using the following IGA scale, at Weeks 8 and 24. The IGA should be representative of the investigator's overall general assessment of the subject's AK and take into account the quality, as well as the quantity, of AK lesions.

Outcome Measure	Score
Completely cleared - Approximately 100% clearance of AK lesions in the treated area	0
Partially cleared - Approximately $\geq 75\%$ clearance of AK lesions in the treated area	1
Moderately cleared - Approximately 50-74% clearance of AK lesions in the treated area	2
Minimally Cleared - Approximately <50% clearance of AK lesions in the treated area	3
Not Cleared - Approximately 0% clearance, i.e., all AK lesions remained in the treated area	4

5.3.2 *Severity of Skin Photodamage*

Site Investigators will be asked to rate the severity of skin photodamage in the AK treated area (at baseline, Weeks 8 and 24), on the following 4-point Likert scale:

Outcome Measure	Score
Absent - Smooth evenly pigmented skin	0
Mild - Freckling and/or other dyspigmentation	1
Moderate - Above plus mildly rough "dry" skin, fine wrinkling and/or telangiectasias or blotchy erythema	2

Severe - Above plus pronounced “dryness” and/or dyspigmentation and/or telangiectasia or erythema, and/or wrinkling, with or without areas of actinic purpura	3
---	---

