Each AE, either serious or non-serious for which a causal relationship to tirbanibulin cannot be excluded, will be considered as an ADR. An ADR is an injury caused by taking medication. ADRs may occur following a single dose or prolonged administration of a medicinal product or result from the combination of two or more medicinal products. LSRs (such as: erythema, flaking/scaling, crusting, swelling, vesiculation/pustulation, and erosion/ulceration), skin scarring and pigmentation (such as: hypo- and hyper-pigmentation) as a result of application of tirbanibulin in AK treatment area will not be considered as ADRs, but will be documented separately.

The determination of whether an AE is related to study treatment (tirbanibulin) will be based on information regarding the degree to which the study treatment had caused or contributed to the event and will be categorized per the following criteria:

- Related: There were good reasons and sufficient information (e.g. plausible time sequence, dose-response relationship, pharmacology, positive de-challenge and/or re-challenge) to assume a causal relationship with the study medication in the sense that it is plausible, conceivable or likely.
- Not Related: There were good reasons and sufficient information (e.g. implausible time sequence and/or attributable to concurrent disease or other drugs) to rule out a causal relationship with the study medication.

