Note: Data from Clinician DCF; X patients had missing data; The denominator for the percentages is the number of patients with available data (N=X). This concomitant non-AK medication use correspond to use of medications at any time during the study observation period, overlapping with Klisyri® medication use.

Table 4.11 Patient Disposition Throughout the Study

	Baseline n (%)		Week 8 n (%)		Week 24 n (%)	
	Patient Survey	Clinician Survey	Patient Survey	Clinician Survey	Patient Survey	Clinician Survey
(Cumulative numbers)						
Patients completing study visit						
Patients with missing surveys						
Patient Terminations/ Discontinuations						
P1Br3 Due to Adverse event associated with any medication (other than tirbanibulin (Klisyri®)						
P1Br4 Due to Adverse drug reaction associated with tirbanibulin (Klisyri®)						
P1Br5 Due to Clinician decision: tirbanibulin (Klisyri®) treatment non-compliance						
P1Br6 Due to Clinician decision, Other [P1Br6oe]						
P1Br2 Patient voluntarily withdrawal of consent (for reasons other than adverse event or adverse drug reaction)						
P1Br1 Patient Lost to follow-up						
TOTAL Study Population (N)	300	300	300	300	300	300

Table 4.12 Reason for Discontinuation

Statistics	Adverse drug reaction associated with tirbanibulin (Klisyri®)	Adverse event associated with any medication (other than tirbanibulin (Klisyri®))	Clinician decision: tirbanibulin (Klisyri®) treatment non-compliance	Clinician decision, Other	Patient voluntarily withdrawal of consent (for reasons other than adverse event or adverse drug reaction)	Patient Lost to follow-up	TOTAL
Week 8	n (%)						
Week 24	n (%)						
TOTAL	n (%)						

Table 4.13 Subject Level Summary of Local Site Reactions

LSRs (Refer to annotated CRF for all other variables)	Baseline N=X	Week 8 N=X	Week 24* N=X
LSR1 Erythema (N=X)			
LSR1r1 Grade			
2. Mild	n (%)	n (%)	n (%)
3. Moderate	n (%)	n (%)	n (%)
4. Severe	n (%)	n (%)	n (%)
LSR1r4 Action taken with Tirbanibulin			
1. Drug withdrawal	n (%)	n (%)	n (%)
2. Dose Reduced	n (%)	n (%)	n (%)
3. Dose Increased	n (%)	n (%)	n (%)
4. Dose not changed	n (%)	n (%)	n (%)
5. Not Applicable	n (%)	n (%)	n (%)
LSR2 Flaking/Scaling (N=X)			
Grade			
Mild	n (%)	n (%)	n (%)
Moderate	n (%)	n (%)	n (%)
Severe	n (%)	n (%)	n (%)
Action taken with Tirbanibulin			
Drug withdrawal	n (%)	n (%)	n (%)
Dose Reduced	n (%)	n (%)	n (%)
Dose Increased	n (%)	n (%)	n (%)
Dose not changed	n (%)	n (%)	n (%)
Not Applicable	n (%)	n (%)	n (%)

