LSR3 Crusting (N=X)			
Grade			
Mild	n (%)	n (%)	n (%)
Moderate	n (%)	n (%)	n (%)
Severe	n (%)	n (%)	n (%)
Action taken with Tirbanibulin			
Drug withdrawal	n (%)	n (%)	n (%)
Dose Reduced	n (%)	n (%)	n (%)
Dose Increased	n (%)	n (%)	n (%)

Dose not changed	n (%)	n (%)	n (%)
Not Applicable	n (%)	n (%)	n (%)

LSR4 Swelling (N=X)**Grade**

Mild	n (%)	n (%)	n (%)
Moderate	n (%)	n (%)	n (%)
Severe	n (%)	n (%)	n (%)

Action taken with Tirbanibulin

Drug withdrawal	n (%)	n (%)	n (%)
Dose Reduced	n (%)	n (%)	n (%)
Dose Increased	n (%)	n (%)	n (%)
Dose not changed	n (%)	n (%)	n (%)
Not Applicable	n (%)	n (%)	n (%)

LSR5 Vesiculation/Pustulation (N=X)**Grade**

Mild	n (%)	n (%)	n (%)
Moderate	n (%)	n (%)	n (%)
Severe	n (%)	n (%)	n (%)

Action taken with Tirbanibulin

Drug withdrawal	n (%)	n (%)	n (%)
Dose Reduced	n (%)	n (%)	n (%)
Dose Increased	n (%)	n (%)	n (%)
Dose not changed	n (%)	n (%)	n (%)
Not Applicable	n (%)	n (%)	n (%)

LSR6 Erosion/Ulceration (N=X)**Grade**

Mild	n (%)	n (%)	n (%)
Moderate	n (%)	n (%)	n (%)
Severe	n (%)	n (%)	n (%)

Action taken with Tirbanibulin

Drug withdrawal	n (%)	n (%)	n (%)
Dose Reduced	n (%)	n (%)	n (%)
Dose Increased	n (%)	n (%)	n (%)
Dose not changed	n (%)	n (%)	n (%)

Not Applicable	n (%)	n (%)	n (%)
LSR7 Scarring			
Present?			
Yes	n (%)	n (%)	n (%)
No	n (%)	n (%)	n (%)
LSR8 Hypo-pigmentation			
Present?			
Yes	n (%)	n (%)	n (%)
No	n (%)	n (%)	n (%)
LSR9 Hyper-pigmentation			
Present?			
Yes	n (%)	n (%)	n (%)
No	n (%)	n (%)	n (%)

Table 4.14 Subject Level Summary of Local Site Reactions, by Patient ID

Patient ID	Study/ Survey Timepoint	LSR	Grade	Date of Baseline (yyyy/mm/dd)	Date of Onset (yyyy/mm/dd)	Status	Action Taken with tirbanibulin*

Table 4.15 Subject Level Summary of Adverse Events, Any Type

Adverse Events, Any Type	N=X n (%)
Subjects with at least 1 adverse event (any type)	
Intensity of adverse event, among Subjects with at least 1 adverse event (any type)	
Mild	
Moderate	
Severe	
Action taken with Tirbanibulin, among Subjects with at least 1 adverse event (any type)	
Drug withdrawal / study discontinuation	
Other Actions:	
Dose Not Changed	
Subjects with at least 1 SAE or Serious ADR	
Subjects with at least 1 SAE or Serious ADR resulting in death	

Table 4.16 Subject Level Summary of 'Not-Related to Tirbanibulin' Adverse Events

'Not-Related to Tirbanibulin' Adverse Events	N=X n (%)
Subjects with at least 1 'not-related' AE	
Intensity of adverse event, among Subjects with at least 1 'not-related' AE	
Mild	

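### Table 4.13 cannot separate local skin reactions that are new or worse since first application from signs already present, and no SAP rule does so

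*SAP*

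**What the plan says.** SAP 6.6.9 gives a descriptive analysis in the Safety Population "to report the frequency of occurrences of AEs, SAEs, ADRs, and LSRs". The summary output is "Table 4.13 Subject Level Summary of Local Site Reactions", with the header "LSRs (Refer to annotated CRF for all other variables) Baseline N=X Week 8 N=X Week 24* N=X". Each column is a separate count of subjects. LSR1 to LSR6 (erythema, flaking/scaling, crusting, swelling, vesiculation/pustulation, erosion/ulceration) are split by grade and by action taken with the drug. LSR7 to LSR9 (scarring and the two pigment changes, for example "LSR8 Hypo-pigmentation") are recorded only as present, yes or no. There is no shift and no row for new or worsened signs. Neither document defines a treatment-emergent LSR.

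Other places bear on how these counts should be read:

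- SAP 5.6.1 (same text in Protocol 8.5.1) describes LSRs, scarring and pigment change as arising "as a result of application of" tirbanibulin.
- Protocol 7.3 has the Week 8 form cover LSRs over the preceding eight weeks, taken from the chart.
- Table 4.14 lists LSRs by patient with time point, grade, date of baseline and a column headed "Date of Onset (yyyy/mm/dd".
- SAP section 4 (Protocol section 7) lets baseline data be collected from 14 days before to 7 days after the index date.
- Protocol 2.1 states that "AK manifests as scaly, red lesions on face, trunk, scalp, and other sun exposed extremities". On the photodamage scale in SAP 5.3.2, score 1 is "Mild - Freckling and/or other dyspigmentation", and score 2 adds mildly rough, dry skin and blotchy erythema, among other signs.

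**The concern.** Patients are enrolled because they have visible AK lesions, and many will also have photodamage. By the documents' own descriptions, such skin can already be red, scaly or unevenly pigmented before any ointment is applied. The same signs appear on the LSR list. A Week 8 count that does not look back at the same patient's pre-treatment state may therefore include disease as well as drug reaction.

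LSR frequency over the first eight weeks is a named additional endpoint (Protocol 3.2, SAP 2.2), and Protocol 2.1 presents milder LSRs as an advantage of tirbanibulin, so the figure is likely to be quoted. The SAP already handles comparable data with more care. It classifies medications by timing relative to the first dose (SAP 6.6.8) and analyses photodamage as change from baseline (SAP 6.6.3). LSRs, which share signs with photodamage, get neither treatment.

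**Working it through.** The plan states no LSR rate and no sample-size calculation, so there is no figure to reproduce. The only input from the documents is the Safety Population of 300 (SAP section 7). All rates below are assumptions.

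**1. What the two columns can show.** Let B be the proportion with a sign at Baseline and W the proportion counted at Week 8, in the same patients. The proportion absent at Baseline and counted at Week 8 satisfies

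max(0, W − B) ≤ new onset ≤ min(W, 1 − B).

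| Assumed B | Assumed W | Lower bound | Upper bound | Patients of 300 |
|---|---|---|---|---|
| 10% | 50% | 50 − 10 = 40% | min(50, 90) = 50% | 120 to 150 |
| 30% | 50% | 50 − 30 = 20% | min(50, 70) = 50% | 60 to 150 |
| 50% | 50% | 50 − 50 = 0% | min(50, 50) = 50% | 0 to 150 |

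The interval is narrow when a sign is rare at baseline and wide when it is common. These bounds hold whether W is a count over the eight weeks or on the day. They concern new onset only; worsening of an existing sign is a further quantity that the table does not show.

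**2. How far the crude count could exceed the treatment-emergent one.** Let b be baseline prevalence, r the proportion with a new or worsened sign (taken as equal in patients with and without the sign at baseline), and q the probability that an unchanged baseline sign is recorded again. Then

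crude Week 8 proportion = r + b(1 − r)q, and excess = b(1 − r)q.

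With b = 30% and r = 30%:

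- q = 0: 30.0%, excess 0.
- q = 0.5: 0.30 + 0.30 × 0.70 × 0.5 = 40.5%, excess 10.5 points (31.5 of 300).
- q = 1: 0.30 + 0.30 × 0.70 = 51.0%, excess 21 points (63 of 300).

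Over b from 10% to 50%, r from 5% to 60% and q from 0 to 1, the excess runs from 0 to 0.50 × 0.95 × 1 = 47.5 points (142.5 of 300). It is 0 whenever q = 0.

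**3. Whether Baseline is a clean reference.** The window is 14 + 7 = 21 days. Five daily applications starting on day 0 end on day 4. A baseline record made on days 0 to +7 can therefore already contain reactions to the drug. A shift from such a record would treat those reactions as pre-existing and under-count LSRs.

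**The case against.** The best reply is the definition. SAP 5.6.1 ties LSRs to application of tirbanibulin, so an unchanged pre-dose sign is not an LSR, and a site that follows the definition will not record it. This stands to the extent that over-counting is a risk and not a certainty. A reader might infer that disease signs will be reported as drug reactions; the documents do not establish that. The definition does not, however, explain the table. If only drug-caused signs were recorded, a pre-dose Baseline column would be empty, yet Table 4.13 gives it full grade rows and rows for action taken. If the column instead holds reactions seen by day +7, it mixes pre-dose and on-treatment records and is no reference. Either way a rule is needed. The annotated CRF named in the table header may contain one, but it is not among the documents.

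A reader might also infer that baseline redness or scaling which clears by Week 8 would offset and hide new reactions. For LSR1 to LSR6 the documents do not support this, because the Week 8 form covers the whole eight weeks and a resolved sign does not drop out. A point-in-time reading is possible only for LSR7 to LSR9.

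Two further replies have some weight. Table 4.13 does print Baseline beside Week 8, and the SAP never proposes subtracting the columns; but separate counts do not give within-patient change. Table 4.14 does give onset dates, so timing can be traced patient by patient; but it is a listing, and no rule carries it into a summary. Finally, the study is single-arm, descriptive and unpowered, with no LSR threshold to pass. That limits the consequence but does not make the frequency interpretable.

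**Conclusion.** The point holds as a gap in the analysis of a named safety endpoint. Neither SAP 6.6.9 nor Table 4.13 separates signs that are new or worse since first application from signs already there, and the overlap of those signs with AK and photodamage is stated in the documents. The size cannot be fixed, because no baseline, onset or re-recording rates are given. Under the assumed rates, the table leaves new onset anywhere within 30 points at B = 30% and W = 50%, and within 10 points at B = 10% and W = 50%. The crude count is not inflated at all if sites never re-record unchanged baseline signs. The conclusion rests on the table layout as drawn, and would weaken if the annotated CRF already tells sites how to handle pre-existing signs.

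**What to change.** In SAP 6.6.9, define a treatment-emergent LSR as a sign absent before first application, or of higher grade after it, with onset on or after first application and within eight weeks. Then:

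- Make this the headline count in Table 4.13, keeping the present columns as supporting detail.
- For LSR1 to LSR6, add a shift from baseline grade to highest recorded post-baseline grade. For LSR7 to LSR9, add a row for new since baseline. Use only baseline records made before first application.
- Report separately the subjects whose baseline was recorded on days 0 to +7 after first application, classifying their signs by the onset dates in Table 4.14. A day-0 record known to precede the first application can stay in the shift.
- State which date marks first application, since SAP section 4 defines the index date as the planned one.

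The cost is one SAP paragraph, one revised table, minor programming and a smaller evaluable set for the shift. The time points, grades and onset dates are already in the planned tables. One check is needed: Protocol 7.1 does not list LSR grading among the baseline items, although Appendix A (footnote 5) and the Baseline column of Table 4.13 imply it, so confirm against the CRF that baseline grades exist.
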